Percent work time missed due to problem:					
Percent impairment while working due to problem					
Percent overall work impairment due to problem					
Percent activity impairment due to problem					
Work & Activity					
Work status – Working					
Hours missed from work in last 7 days because of problem- Mean (SD)					
Hours missed from work in last 7 days for other reasons- Mean (SD)					
Hours worked in last 7 days for other reasons - Mean (SD)					
Joint and muscle symptoms affect your productivity while working - Mean (SD)					
Joint and muscle symptoms affect ability to do regular daily activities, other than work - Mean (SD)					

Patient Experience at 3 months

As a result of your visit are you accessing less or more NHS care? b [no baseline]					
Much more care					
More care					
About the same care					
Less care					
Much less care					
Prefer not to say					
Patient thoughts about the MSK Tracker System					
How useful did you find it?					
Very useful					
Useful					
Uncertain					
Not useful					
Not useful at all					
Prefer not to say					
How easy was it to use?					
Very easy					
Easy					
Uncertain					
Not easy					
Not easy at all					
Prefer not to say					
How well did it help you think about the issue related to the care for your joint and muscle symptoms?					
Very well					
Well					
Uncertain					
Not well					
Not well at all					
Prefer not to say					
Did it increase any stress associated with your appointment?					
Yes - increased stress a lot					
Yes - increased stress a little					
Made no difference					
No - it reduced stress a little					
No - it reduced stress a lot					

10. Appendices

Figure 1 - Consort diagram

[figure not shown]

Figure 2 - Study Flow chart

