	
recruited to take part in an interview about their current practice.
 
 - Phase 2 will recruit approximately 40 patients in up to 2 cycles of approximately 20 to complete the quantitative online survey, with up to 20 of these patients interviewed about their experiences (up to 2 cycles of approximately 10 patients). In addition, up to 10 clinicians will also be recruited to take part in a feedback workshop or individual interview about their experiences of the MSK-Tracker. - Phase 3 will recruit approximately 200 patients to complete the quantitative online survey with 10 of these patients also interviewed about their experiences. In addition, up to 10 clinicians will also be recruited to take part in a feedback workshop or individual interview about their experiences of the MSK-Tracker. 
In total the expected accrual figure for this project is approximately 440 patients consenting to take part in the MSK Tracker study with approximately 10 clinicians taking part in qualitative research.

Treatment duration	Patients will not receive any additional treatments in this study.
Follow up duration	In all three phases patients will complete the cohort follow-up surveys at 2 weeks and 3 months after their initial clinic consultation.
Planned Study Period	It is expected that recruitment for phase 1 will be staggered over the two NHS Trusts. The first Trust is expected to have completed phase 1 by Nov 2018, then to have a few months of Phase 2 and then to begin Phase 3 in spring 2019. At the second trust we expect to begin phase 1 in Jan 2019 and phase 3 around 2 months later. .

	Objectives	Outcome Measures
Primary	To improve patient self-reported measures of empowerment	A measure of patient empowerment - the patient enablement scale, will be the primary outcome in this study

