6 ELIGIBILITY CRITERIA

6.1 Inclusion criteria

Patients aged 18 years and above with an appointment at one of the participating services for an MSK pain problem will be invited to take part.

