8.2 Planned recruitment rate

The target recruitment will be 200 participants (in both phase 1 and phase 3).

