The study is using a 'before' and 'after' sequential comparison design with an iterative pilot and user testing phase in between. In addition, audio recordings of the consultation (in a sub-sample, n=40 (phase 1=20 & phase 3=20)), alongside individual clinician (n=10) and patient interviews and a feedback workshop with clinicians and patients, will explore the feasibility, and impact of implementing the MSK-Tracker within routine consultations and user experiences. The study will take place in Staffordshire Musculoskeletal Interface Service based at Haywood Hospital in Burslem, Stoke-on-Trent.

3. Study and evaluative population

Patients aged 18 years and above with an appointment to attend the Staffordshire Musculoskeletal Interface Service for an MSK pain problem will be invited to take part. Patients unable to use or access the internet will be unable to take part in this research as well as patients who do not provide informed consent for study participation and data collection. The online system will only be available in English.

Phase 1 ('Before' stage). Patients (n=120) who meet the eligibility criteria for having long-term MSK pain will consent online and complete an electronic survey shortly before their consultation. This phase will not utilise the new innovative 'MSK-Tracker' online components, in order to give a baseline comparator. Patients will complete follow-up data 2 weeks and 3 months after their clinic date and clinicians will complete a case report form (CRF) using the clinician portal. Audio recordings of approximately 20 patient consultations will examine consultation conversations and their content using discourse analysis.

Phase 2. ('Pilot stage'). Phase 2 will focus on pilot testing the MSK-Tracker components including the, pre-clinic preparation survey, clinician dashboard, summary action plan, patient's goal setting module, follow-up survey and progress charts. The study will seek to refine the processes used in phase 3, with a limited number of patients (approximately 40 patients in 2 cycles of 20) and clinicians (n=10) using the Tracker.

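### The SAP restricts the evaluated population and the PEI to the Staffordshire service, while the protocol recruits at two NHS Trusts; neither document puts Trust into the primary comparison

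*SAP*

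**What the plan says.** **SAP.** Section 2 gives a single setting: "The study will take place in Staffordshire Musculoskeletal Interface Service based at Haywood Hospital in Burslem, Stoke-on-Trent". Section 3, which defines the evaluative population, invites patients "with an appointment to attend the Staffordshire Musculoskeletal Interface Service for an MSK pain problem will be invited to take part". Section 5 describes the PEI as a rating of the effect of a visit to that same service. No second site appears anywhere in the SAP. The primary analysis in section 7 is an unadjusted two-sample t-test of Phase 1 against Phase 3. The baseline tables in section 9 have no row for Trust or site.

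**Protocol.** The synopsis (Planned Study Period) states: "It is expected that recruitment for phase 1 will be staggered over the two NHS Trusts". The first Trust is to finish Phase 1 by November 2018 and begin Phase 3 in spring 2019. For the other: "At the second trust we expect to begin phase 1 in Jan 2019 and phase 3 around 2 months later". Section 6.1 admits patients "with an appointment at one of the participating services for an MSK pain problem". Section 7.6.1 places Phase 2 at the first site only. Section 8.2 sets one number per phase: "The target recruitment will be 200 participants (in both phase 1 and phase 3"). No Trust-level target is given.

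The protocol is not consistent with itself either. The sample-size text in section 8.1 still ties the PEI to the Staffordshire service alone. Section 8.3 allows adjustment for important differences between the phases where appropriate, without naming Trust.

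**The concern.** The evaluative population decides who enters the primary comparison, and here it can be read in two ways.

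- **Literal reading.** Only Staffordshire patients count, so patients whom the protocol recruits at the other Trust fall outside the primary analysis.
- **Pooled reading.** Both Trusts are analysed together by a t-test that ignores Trust. The comparison is before versus after, not randomised, so a change in the Trust mix between phases feeds directly into the phase difference whenever the Trusts differ in mean PEI.

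The timetable makes some change in mix plausible. In Phase 1 the first Trust is due to finish before the second opens. In Phase 3 the two Trusts start at roughly the same time and fill one shared total. Nothing in either document fixes the shares, and with no Trust row in the baseline table a shift would not be displayed.

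**Working it through.** **1. The plan's own figure.** Inputs from SAP 5 and Protocol 8.1: effect size 0.40, SD 3.86, two-sided 5%, 80% power. The difference is 0.40 × 3.86 = 1.544, stated as 1.55. The normal approximation gives 99 per phase and the noncentral t gives 99.08, which rounds up to the stated 100. Power at 100 per phase is 80.4%. The figure reproduces, and the point does not depend on it.

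**2. The two documents side by side.**

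| Item | SAP | Protocol |
|---|---|---|
| Setting | Staffordshire service (section 2) | Two Trusts (synopsis); participating sites (section 5) |
| Population | Patients of that service (section 3) | Patients of any participating service (6.1) |
| PEI refers to | That service (section 5) | That service (8.1) |
| Target per phase | 120, with 20% loss (section 5) | 200, with 50% loss (8.1, 8.2) |
| Split by Trust | None | None |
| Trust in primary analysis | None (section 7) | Not named; conditional adjustment (8.3) |

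The differing targets suggest that the SAP was not brought into line with the two-Trust protocol.

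**3. Bias if the Trusts are pooled without adjustment.** Bias = (change in Trust share between phases) × (difference in mean PEI between Trusts). Neither input is in the documents. Assumed for illustration: a shift of 0.20 to 0.30 and a difference of 0.5 to 1.5 points.

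- Low end: 0.20 × 0.5 = 0.10 points; 0.10 / 1.55 = 6% of the target difference.
- High end: 0.30 × 1.5 = 0.45 points; 0.45 / 1.55 = 29%.
- Equal shares, or no Trust difference: 0.

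With 100 analysed per phase, SE = 3.86 × √(2/100) = 0.546. With no true effect, the type I error is Φ(bias/SE − 1.96) + Φ(−bias/SE − 1.96). At 0.10 points (0.18 SE) it is 5.4%. At 0.45 points (0.82 SE) it is 13.1%.

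**4. Cost of adjusting for Trust.** Combine the within-Trust differences with inverse-variance weights. With n₁ and n₃ the Phase 1 and Phase 3 numbers analysed at a Trust, w = Σ n₁n₃/(n₁ + n₃) over Trusts, SE = 3.86/√w, and power = Φ(1.544/SE − 1.96).

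- One Trust with 50% of both phases: w = 25 + 25 = 50, SE 0.546, power 80.7%.
- One Trust with 60% of Phase 1 and 40% of Phase 3: w = 24 + 24 = 48, SE 0.557, power 79.1%.
- 70% and 40%: SE 0.573, power 76.9%.
- 75% and 25%: SE 0.630, power 68.8%.

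**The case against.** **The bias is hypothetical.** No document says that the Trusts differ in case mix, referral routes or PEI. A 1.5-point gap would be nearly as large as the whole target difference, and at the low end the type I error barely moves. This stands: the figures illustrate and do not estimate. It does not remove the gap, because the plan neither controls nor displays the Trust mix.

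**Partial safeguards exist.** Protocol 8.3 permits adjustment, and SAP 6 compares baseline characteristics, including referral source, problem duration, pain location and comorbidities. These could pick up part of a site effect. But 8.3 is conditional and does not name Trust, the SAP's primary test does not carry the adjustment over, and the baseline table omits Trust.

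**Stronger readings that the documents do not support.**

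- A reader might infer that applying the SAP population cuts power to about 51%. That takes the SAP's single service together with the protocol's 200 and 50% loss, plus an assumed half-and-half split. On the SAP's own plan, 120 × 0.80 = 96 per phase remain, with power of about 79% for d = 0.40. The conflict between 20% and 50% loss is a separate matter.
- A reader might infer that one phase could fill mainly at one Trust and the other phase mainly at the other. The synopsis schedules both phases at both Trusts, so some imbalance is possible but a near-complete reversal is not implied.
- A reader might treat this as a fault of the SAP alone. Protocol 8.1 carries the same single-service wording.

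**Conclusion.** The inconsistency is in the operative text and should be corrected. SAP 2, 3 and 5 and Protocol 8.1 describe one service, while the rest of the protocol describes recruitment at two Trusts. Until this is settled, it is unclear who belongs in the primary comparison. If both Trusts are pooled, the SAP's t-test has no protection against confounding by Trust.

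The size cannot be determined from the documents. The range of 0.10 to 0.45 points rests entirely on the assumed share shift and PEI difference, and the true value may be zero. No loss of power from the site definition is established. The case for change rests on the unclear population and the unprotected comparison, and the remedy is cheap.

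**What to change.** 1. Amend SAP 2, 3 and 5 and Protocol 8.1 so that setting and population cover eligible patients at every participating Trust, and the PEI refers to the service the patient attended.
2. In SAP 7, prespecify Trust as a stratum or covariate in the primary PEI comparison, so that the phase effect is estimated within Trust.
3. Add Trust as a row in the SAP baseline table, by phase.
4. Optionally, aim for balanced recruitment per Trust within the same total. Keep this as an aim and not a closing rule: matching enrolled numbers does not match 2-week responders when 50% loss is planned, and closing a Trust early could leave Phase 3 short of 200.

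**Cost.** Items 1 and 3 are wording and one table row. Item 2 loses a little precision if shares are unequal: about 79% power if a Trust supplies 60% of one phase and 40% of the other, against 80.7% with equal shares. The loss grows with the imbalance (68.8% at 75% and 25%), which is the reason for item 4. The total sample size does not change.

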8 STATISTICS AND DATA ANALYSIS

8.1 Sample size calculation

The primary outcome of this trial is the patient enablement instrument (PEI) at 2 week follow up. As patients are asked to retrospectively rate the level of enablement, at the 2-week follow up, as a result of their visit to the Staffordshire Musculoskeletal Interface Service we only have a score at a single time point (and not a change score) for each group of patients in Phase 1 and Phase 3. The Patient Enablement Instrument consists of six items graded on three-point scales. It is scored between 0 and 12 and a high score represents more enablement. The sample size was generated based on that required for an independent groups two-sample t-test with a two tailed 5% significance level at 80% power. As no Minimally Clinically Important Difference (MCID) relevant to the specific context could be found for the PEI, the study is powered to find a 0.40 effect size – representative of a small to medium effect. The expected SD for the population is 3.86 thus, the implied MCID between the groups would be a score of 1.55 scale points. Accordingly, the required sample is 100 in each arm. If we account for 50% dropout and missingness, the target recruitment is 200 in both phases 1 and 3.

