The primary outcome of this trial is the patient enablement instrument (PEI)¹ at 2 week follow up. As patients are asked to retrospectively rate the level of enablement, at the 2-week follow up, as a result of their visit to the Staffordshire Musculoskeletal Interface Service we only have a score at a single time point (and not a change score) for each group of patients in Phase 1 and Phase 3. The Patient Enablement Instrument consists of six items graded on three-point scales. It is scored between 0 and 12 and a high score represents more enablement. The sample size was generated based on that required for an independent groups two-sample t-test with a two tailed 5% significance level at 80% power. As no Minimally Clinically Important Difference (MCID) relevant to the specific context could be found for the PEI, the study is powered to find a 0.40 effect size – representative of a small to medium effect.² The expected SD for the population is 3.86¹ (taken from Howie et al. 1998) thus, the implied MCID between the groups would be a score of 1.55 scale points. Accordingly, the required sample is 100 in each arm. If we account for 20% dropout and missingness, the target recruitment is 120 in both phases 1 and 3.

6. Participant characteristics

Baseline characteristics for participants will be displayed in relation to the two groups of participants, i.e., those who are enrolled Phase 1 and those who are enrolled in Phase 3. Given the fact that patient groups are not randomly allocated hypothesis testing will be done comparing the groups at baseline for comparability.

See Tables in section 9 for details of which variables will be collected and how they will be reported.

7. Methods of analysis

Descriptive statistics:

For all outcomes, numerical variables will be summarised as either mean (SD) or median (IQR) depending on the skew of the distribution of the variable in question. Categorical variables will be described as frequencies and percentages.

Primary outcome measure:

A two-tailed independent sample t-test will be conducted to compare the mean PEI score in Phase 1 with that in Phase 3. An effect size, Cohen's Delta, and 95% confidence intervals will be reported for the mean difference between scores. A p-value will be reported with a significance level rate of < 5% leading to a rejection of the null hypothesis of no difference between the two groups.

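### The SAP's target of 120 per phase leaves 96, not 100, at its own 20% loss, and it conflicts with the protocol's 200 per phase at 50% loss

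*SAP*

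**What the plan says.** Both documents size the study on the Patient Enablement Instrument (PEI) at 2 weeks, comparing phase 1 with phase 3. SAP section 5 bases the calculation on "an independent groups two-sample t-test with a two tailed 5% significance level at 80% power" and says "the study is powered to find a 0.40 effect size". Protocol section 8.1 uses the same test and effect size. It adds "The expected SD for the population is 3.86", a value the SAP shares. Each document arrives at 100 patients per phase.

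They part company at the allowance for loss:

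- SAP section 5: "If we account for 20% dropout and missingness, the target recruitment is 120 in both phases 1 and 3". SAP section 3 repeats the number for phase 1: "Patients (n=120) who meet the eligibility criteria for having long-term MSK pain". It describes phase 3 as mirroring phase 1.
- Protocol section 8.1: "If we account for 50% dropout and missingness, the target recruitment is 200 in both phases 1 and 3". Section 8.2 repeats 200 for both phases. The synopsis and section 4 also give 200 or approximately 200, and the synopsis total of approximately 440 equals 200 + 40 + 200.

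**The concern.** There are two faults. First, the SAP's recruitment target does not follow from its own requirement and its own loss rate. Adding 20% to the number needed is not the same as allowing for the loss of 20% of those recruited.

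Second, the protocol and the SAP start from identical inputs and end with different loss rates and targets, and neither text explains this or says which prevails. A reader cannot tell what was prespecified for the primary endpoint, which is the one outcome with a stated power calculation. If the trial were run to the SAP target and lost patients at the rate the protocol expects, the primary comparison would be well short of its stated power.

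**Working it through.** **Inputs** (SAP section 5 and protocol section 8.1, identical unless noted): two-sample t-test, two-sided alpha 0.05, power 0.80, standardised effect d = 0.40, SD 3.86. Loss is 20% in the SAP and 50% in the protocol. Recruitment per phase is 120 in the SAP and 200 in the protocol.

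**Step 1. Reproduce the 100 per phase.**

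- Implied difference: 0.40 × 3.86 = 1.544 points (the documents give 1.55).
- Normal approximation: n = 2(1.960 + 0.842)² / 0.40² = 98.1, so 99 per phase.
- Exact t-test: 99.1, so 100 per phase.

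The stated 100 is sound.

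**Step 2. Allow for loss.** To retain n after a proportion L is lost, recruit n / (1 − L).

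| Document | Loss L | 100 / (1 − L) | 100 × (1 + L) | Stated |
|---|---|---|---|---|
| SAP | 0.20 | 125 | 120 | 120 |
| Protocol | 0.50 | 200 | 150 | 200 |

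The protocol's figure follows from the correct formula. The SAP's figure follows only from the incorrect one. Rounding does not explain it: starting from 99 gives 124, and starting from 98 (using the rounded 1.55) gives 123.

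**Step 3. What each target leaves, and the power** (t-test, d = 0.40):

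| Recruited | Loss | Analysed per phase | Power |
|---|---|---|---|
| 200 (protocol) | 50% (protocol) | 200 × 0.50 = 100 | 80.4% |
| 120 (SAP) | 20% (SAP) | 120 × 0.80 = 96 | 78.7% |
| 120 (SAP) | 50% (protocol) | 120 × 0.50 = 60 | 58.4% |

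Recruiting 120 leaves 100 only if loss is no more than 1 − 100/120 = 16.7%.

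**Step 4. Difference detectable with 80% power.** It is about 1.54 points at 100 per phase, 1.57 at 96 and 1.99 at 60.

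**Step 5. Total recruitment.** The SAP's phases sum to 120 + 40 + 120 = 280. The protocol's sum to 200 + 40 + 200 = 440, which is 160 more.

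**The case against.** - **The slip is minor.** It costs four analysable patients per phase and under two points of power, and the detectable difference moves only from 1.54 to 1.57 points. The effect size is itself a convention, since the documents found no minimally important difference suited to this setting. This is right as far as the slip alone goes.
- **The 58.4% combines figures that neither document pairs.** This is also right. It is conditional on recruiting to the SAP target and losing patients at the protocol rate. Under the protocol's own plan no power is lost. The figure shows what is at risk while the conflict stands; it does not describe the planned power.
- **The SAP may simply be older.** The supplied text cannot settle the order of the two documents. An outdated SAP would still need updating.
- **Multiple imputation could offset the loss.** SAP section 7 plans it for missing PEI scores but does not offer it as a reason for a smaller target. There is no baseline PEI to impute from, so little of the lost information is likely to be recovered.
- **Neither loss rate is justified.** This stands: no source is given for 20% or for 50%. It argues for stating a basis, not for leaving two rates in place.
- **An edit now could be retrospective.** The table shells in SAP section 9 already carry case report form counts (93 in phase 1, 83 in phase 3) and a conclusion of no difference. These are not PEI completers, but some results may have been known. This stands as a reason to date and label the change.

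**Conclusion.** The concern holds on both counts. On the SAP's own inputs, 120 per phase leaves 96 and gives 78.7% power, short of the stated 80%; the figure should be 125. Separately, the SAP's 120 at 20% loss and the protocol's 200 at 50% loss cannot both be the plan. The conflict is the more serious part: with 120 recruited and 50% lost, power would be 58.4% and the detectable difference 1.99 points. The protocol's own figures are consistent and deliver 80.4%.

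These results assume equal numbers in the two phases, an SD of 3.86, d = 0.40, and an analysis of patients with an observed 2-week PEI. They do not show that 50% is the right loss rate, only that the two documents disagree and that the SAP's target fails at either rate.

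**What to change.** Restate SAP sections 3 and 5 to match the protocol: 50% dropout and missingness, 200 recruited and 100 analysed in each of phases 1 and 3. Give the basis for the 50%. If 20% is kept anywhere, state 125 per phase (100 / 0.80) and justify departing from the protocol's rate.

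In the same edit, align the setting. SAP sections 2 and 3 name a single service, while the protocol synopsis describes two NHS Trusts; the wording in protocol section 8.1 also still refers to the single service. Date the change and say whether any outcome data had been seen when it was made.

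The cost is a revision of wording. The protocol already plans 200 per phase, so aligning to it requires no patients beyond that plan.

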8.3 Statistical analysis plan

Initially, descriptive data will characterise the study sample. A descriptive statistical analysis will provide estimates of the extent to which, between phase 1 and phase 3, the use of the MSK-Tracker changed the content and time spent on topics of patient concern in the clinic consultations. A formal hypothesis testing of the effectiveness of the MSK-Tracker to empower patients using the patient

enablement scale will be conducted. Estimates of mean differences will be calculated between phase 1 and phase 3 with 95% confidence intervals (and with adjustment for any important differences between phase 1 and phase 3 participants, if appropriate). Additionally, by calculating between-group effect sizes on a range of clinical outcomes, the analysis will seek to identify on which outcomes the MSK-Tracker implementation has had impact. If a clinically meaningful difference on an outcome lies within the confidence interval, this will support evidence of an effect of the MSK-Tracker. Changes in clinician behaviours reported on the case report forms will be examined to test if there are significant differences in these behaviours between 'before' and 'after' phases i.e. phase 1 and phase 3.

Feasibility will be determined if greater than 50% of both patients and clinicians agree that the MSK-Tracker is acceptable and useful in routine clinical care based on items in the 3 month follow-up questionnaire to patients, and the interviews with patients and clinicians in phase 3.

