Phase 3 ('After' stage). Stage 3 will mirror Phase 1, ***with newly recruited patients***, except the final MSK-Tracker components will be used. As in phase 1, audio recordings of approximately 20 patient consultations will examine consultation conversations and their content. In addition, a report will be produced for the clinical managers about their service outcomes and areas of unmet need in order to inform quality improvement with a workshop planned to better understand what information services find most useful.

4. Outcomes

For each of the study Phases (1-3), taken at Baseline, Two-week follow-up and/or three month follow up (see section 9 for details on the specific measures collected at each time point).

Baseline measures:

- A range of patient self-report characteristics to be able to describe the patient population such as age, gender, ethnicity, education level, work status, health literacy, MSK pain site/condition, and episode duration. **See Tables in section 9 of this document.**

Primary outcome measure:

- The Patient Enablement Index (PEI)

Secondary outcome measures:

- A number of secondary outcomes will be collected including: MSK-HQ score, Consumer Health Activation Index score, consultation experience measures, work status and impressions of the MSK-tracker system. **See Tables in section 9** for full details of these outcomes and how they will be reported.

Feasibility outcomes:

- A range of feasibility outcomes will be reported, including: numbers of participants completing each stage of the study, details around study registration, 2-week follow-up and 3-month follow-up, timing of and time taken to complete study survey components. **See Tables section 9** for full details of what feasibility information will be collected and how it will be reported.

5. Sample size

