Model residuals will be checked for normality, if deviation is found appropriate transformations will be made to the PEI score. Exploration of patterns of missingness will be undertaken to look for potential associates with baseline. Under the assumption of Missing at Random (MAR) missing data on the primary outcome measure will be imputed via the multiple imputation by chained equation (MICE) method³. Sensitivity analysis will be conducted to assess impact of the MAR assumption. Analyses will be done with missing values both ± 1.55 scale points (the implied MCID) on the PEI – to model the potential effect of Missing Not at Random Bias (truncated between 0 – 12).

Secondary outcome measures:

Secondary outcome measures will be analysed via t-test. Effect sizes and 95% confidence intervals will be reported for all measures. P-values will be reported and a <5% rejection criterion will be utilised. No sensitivity analyses will be undertaken and no corrections for multiplicity will be made for the secondary outcomes.

Feasibility outcomes:

Only descriptive statistics for the feasibility outcomes will be reported. These will be counts and percentages with an appropriate denominator for each measure.

Technical details:

It is envisioned that R (current version 3.5.1) will be used for all analyses. The primary outcome will be analysed by the two study statisticians, unblinded. The statistical analyses and associated datasets will be kept in the appropriate section of the trial master file on the internal secure network.

8. References

1. Howie JG, Heaney DJ, Maxwell M, Walker JJ. A comparison of a patient enablement instrument (PEI) against two established satisfaction scales as an outcome measure of

primary care consultations. *Fam Pract.* 1998;15(2):165-171.

2. Cohen J. A Power Primer. *Psychol Bull.* 1992;112(1):155-159.

9. Tables/Figures

Feasibility/process outcomes

Potential participants	Phase 1 (before)	Phase 3 (after)	Total
Number of patients invited to take part			
Actual participants:			
Study consent & Completed baseline survey			
Consultation audio recording			
Clinician completed case report form in clinic			
Patient received clinic summary action plan			
Accessed goal setting module			
Patient completed 2-week FU survey			
Patient needed a reminder email for 2-week FU survey			
Patient completed 3-month FU survey			

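### The SAP tests 2-week PEI with an unadjusted t-test between non-randomised phases and does not carry over the Protocol's conditional, unspecified covariate adjustment

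*SAP*

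**What the plan says.** SAP section 7 gives one comparison for the primary outcome: "A two-tailed independent sample t-test will be conducted to compare the mean PEI score in Phase 1 with that in Phase 3". An effect size, a 95% confidence interval and a p-value judged at 5% go with it. The same section adds a residual check with possible transformation, multiple imputation of missing PEI, and a sensitivity step: "Analyses will be done with missing values both ± 1.55 scale points (the implied MCID) on the PEI". It also says: "The primary outcome will be analysed by the two study statisticians, unblinded".

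SAP section 3 describes Phase 3 as mirroring Phase 1 "with newly recruited patients". SAP section 6 recognises what follows from this: "Given the fact that patient groups are not randomly allocated hypothesis testing will be done comparing the groups at baseline for comparability". It does not say what happens if those tests show a difference.

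Protocol 8.3 announces "A formal hypothesis testing of the effectiveness of the MSK-Tracker to empower patients" and plans mean differences with 95% confidence intervals, "with adjustment for any important differences between phase 1 and phase 3 participants, if appropriate". It lists no covariates and gives no rule for deciding when a difference is important or when adjustment is appropriate.

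**The concern.** In a before-and-after comparison of separate patients, nothing in the design balances case mix. PEI is measured only after the visit, so there is no baseline PEI to adjust for. Other baseline variables must do that work, and the SAP's primary analysis uses none of them.

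Two different harms follow, depending on which document is applied.

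- **SAP as written.** Any measured difference between phases in a variable related to PEI passes into the estimated effect of the tracker and into its p-value. Protocol 7.3 and Table 1 show that MSK-HQ, CHAI, age, gender and episode duration are collected before the clinic visit in all phases.
- **Protocol clause.** Adjustment is possible, but the covariates and the trigger remain open while the analysts are unblinded.

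The Protocol presents this comparison as a formal test of effectiveness, so either harm bears on the study's main claim.

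**Working it through.** **Inputs from the documents (SAP section 5, Protocol 8.1).** SD 3.86; effect size 0.40; target difference 1.55 points; 100 evaluable per phase; two-sided 5%; 80% power. Recruitment is 120 per phase in the SAP and 200 in the Protocol.

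**1. The plan's own figure.** 0.40 × 3.86 = 1.544, close to the stated 1.55. An exact two-sample t-test needs 99.08, so 100 per phase; power at 100 is 80.4%. The sample size reproduces and is tied to the unadjusted t-test.

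**2. Bias of the unadjusted difference.** Assume no tracker effect, and one covariate whose mean differs by d SD between phases and which correlates r with PEI. The documents give neither d nor r.

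- SE = 3.86 × √(2/100) = 0.546
- Bias b = d × r × 3.86
- Rejection rate = Φ(−1.96 + b/SE) + Φ(−1.96 − b/SE)

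| d | r | Bias (points) | Share of 1.544 | Rejection of a true null |
|---|---|---|---|---|
| any | 0 | 0 | 0% | 5.0% |
| 0.1 | 0.2 | 0.08 | 5% | 5.2% |
| 0.2 | 0.2 | 0.15 | 10% | 5.9% |
| 0.2 | 0.3 | 0.23 | 15% | 7.1% |
| 0.2 | 0.5 | 0.39 | 25% | 10.9% |
| 0.3 | 0.3 | 0.35 | 22.5% | 9.8% |
| 0.4 | 0.5 | 0.77 | 50% | 29.3% |

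**3. Does the imputation deal with it?** No; it fills in missing PEI and leaves the phases unbalanced. In simulation (d = 0.2; normal PEI without the 0–12 bounds; PEI missing completely at random and equally in both phases; 100 observed of 120 or of 200; covariate in the imputation model), the t-test after imputation had bias of 0.23 to 0.24 at r = 0.3 and 0.38 to 0.39 at r = 0.5. Rejection was about 7% and 11%. Regression adjusted for the covariate had bias within 0.01 and rejection of 4.7% to 4.9%. Leaving the covariate out of the imputation model brought part of the bias back: 0.04 to 0.07 points at 17% missing and 0.12 to 0.19 at 50% missing.

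**4. Do the baseline tests deal with it?** The SAP attaches no action to them, and they detect modest imbalance poorly. Power to detect 0.2 SD is 29%, 34% and 51% at 100, 120 and 200 per phase.

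**5. Cost of adjusting.** CHAI, MSK-HQ, age and gender take about one coefficient each. Episode duration has seven categories in the SAP shell and takes six, so about ten in all. With 200 analysed, chance imbalance inflates the variance by 197/187 = 1.053. Power for 0.40 SD is then 78.3% if the covariates explain nothing, and 80.3% if they explain 5% of PEI variance.

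**The case against.** The strongest reply is that the SAP does not withdraw the Protocol's adjustment; it is silent on it. Nothing in the available text sets precedence, and the front pages were not available. A reader might infer that the study has decided against adjustment. The documents do not support that; they support only a disagreement between the two texts.

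If the Protocol clause is applied, the bias may be small. Under an assumed rule of adjusting when a baseline test gives p < 0.05, simulation with d = 0.2 and r of 0.3 to 0.5 leaves 0.07 to 0.16 points and 5.2% to 5.6% rejection. This stands. On that route the problem is the free choice of covariates more than bias.

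It is also fair that d and r are assumed. Eligibility is the same in both phases, and PEI is a retrospective rating of the visit, so a strong relation to baseline status cannot be presumed. The honest range runs from nil to material.

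A reader might also say that the ±1.55 analyses leave the bias exactly unchanged. The SAP truncates the shifted values to 0–12, so that is not correct. Assume imputed values with mean 4 (the GP reference in the SAP shells) and SD 3.86, and the same shift and missingness in both phases. The proportion inside the bounds is then 0.877 after +1.55 and 0.731 after −1.55. The bias shrinks by the missing fraction times the remainder: 2.0% and 4.5% at one-sixth missing, 6.1% and 13.5% at half missing. That is incidental; those analyses still do not address confounding.

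**Conclusion.** The point holds as a gap in specification. The SAP's only comparison of PEI between phases is unadjusted, the SAP says allocation is not random, and the Protocol's conditional adjustment is neither carried over nor defined.

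The consequence cannot be sized from the documents. With assumed imbalance of 0.1 to 0.2 SD and correlation of 0.2 to 0.5, at 100 per phase, the bias is 0.08 to 0.39 points and the false-positive rate 5.2% to 10.9%. Both are nil or nominal when r = 0, and larger with greater imbalance.

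Two further inferences should be resisted. Unblinded analysis, and the patient counts and comments left in the SAP shells, do not show that PEI by phase was seen before the plan was fixed: the counts head the clinician form, the written conclusion follows the baseline table, and the remark about a high score concerns the Valuing Patients scale. Nor would adjustment make the comparison causal, because calendar-time changes and unmeasured differences between phases remain. The pre-written conclusion in the shells, and the question of one service or two Trusts, are separate matters.

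**What to change.** In SAP section 7, make the primary analysis a linear regression of 2-week PEI on phase plus CHAI, MSK-HQ, age, gender and episode duration, all at baseline. Include them whatever the baseline tests show.

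- Put the same covariates in the imputation model.
- Run the ±1.55 analyses on the adjusted model, and apply the residual check to it.
- Keep the unadjusted t-test as a supporting analysis.
- Align Protocol 8.3 with this text.
- State that adjustment does not remove calendar-time or unmeasured confounding.
- If PEI by phase has already been seen, label the adjusted model post hoc.

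The cost is SAP and Protocol wording and a few lines of R, with no new data. The headline estimate becomes model-based and no longer matches the t-test behind the sample size. Power at 100 per phase falls from 80.4% to 78.3% if the roughly ten coefficients explain nothing, and is 80.3% if they explain 5% of PEI variance. If the data have been seen, the adjusted result cannot be called pre-specified.
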